7.6 Hearing loss

Sensorineural hearing loss has rarely been reported in patients receiving high doses of DFO long-term. One study assessed the frequency of hearing loss cross-sectionally in 67 patients receiving regular DFO via subcutaneous pump infusion for β-thalassemia.¹¹⁰ Patients received DFO at a mean dose of 50 mg/kg/day. In five patients, sensorineural hearing loss was detected. The mean exposure time to DFO in these five patients was 15 years. Importantly, hearing loss has not been reported with short-term use of DFO for acute organ injury prevention (**Table 3**). The largest such study, a phase 2 RCT of DFO at 32 mg/kg per day for 3 days in patients with ICH, found the incidence of hearing loss was similar in DFO- and placebo-treated patients (1 of 144 [1%] and 1 of 147 [1%], respectively).⁸²

7.7 Summary of all potential adverse effects of DFO, and their frequency

Very common side effects (affecting more than 1/10 patients):

- Injection site reaction such as pain, swelling, reddening, itching of the skin
- Joint or muscle pain

Common side effects (affecting between 1/10 to 1/100 patients):

- Nausea
- Headache
- Fever

Uncommon side effects (affecting between 1/100 to 1/1,000 patients):

- Vomiting
- Abdominal pain
- Disturbances of hearing such as ringing, hearing loss

Rare side effects (affecting between 1/1,000 to 1/10,000 patients):

-Disturbances of vision such as blurred eyesight, abnormal color vision, night blindness, black spots in the vision, loss of vision, clouding of the lens of the eye, visual field defects, or decreased sharpness of vision

-Fungal or bacterial infections leading to high fever, shortness of breath, acute diarrhea, abdominal pain, general discomfort, or sore throat

-Dizziness, light-headedness (signs of low blood pressure that can occur when the drug is given too rapidly)

Very rare side effects (affecting less than 1/10,000 patients):

-Diarrhea

-Sensation of numbness or tingling in fingers and toes

-Breathlessness due to lung disorders

-Hives, difficulty breathing or swallowing, feeling of tightness in the chest with wheezing or coughing, dizziness, swelling mainly of the face and throat (signs of a severe allergic reaction or asthma)

-Disturbances of the nervous systems

Unknown frequency:

-Muscle spasms

-Abnormal kidney function test results or decreased urine output

Additional information on DFO safety can be found in the attached FDA product label.

7.8 Risks of blood draw

The total volume of blood collected for this study (assuming that a subject is hospitalized for at least 2 days postoperatively) is 80mL (about 5 tablespoons). Blood will be obtained from arterial or central venous catheters, which are inserted preoperatively as part of routine clinical care. If, during the course of the study, neither an arterial nor central venous catheter remains in place, blood will be obtained by peripheral venipuncture by a phlebotomist, in which case all efforts will be made to time the blood collection with a clinical blood draw to minimize discomfort. There is a very small risk of infection, lightheadedness, and/or fainting during blood draws.

7.9 Loss of confidential patient information

Loss of confidential patient information is a potential risk in any clinical study. To minimize this risk we will collect our primary database using REDCap, a secure, HIPAA-compliant, web-based application for building and managing databases. REDCap has many advanced features including multi-site access, audit trails, and the ability to export data with removal of identifiers. Electronic study documents containing protected health information will only be kept on password-protected hospital computers. Paper documents containing protected health information will be kept in binders stored in a secure location at each hospital site. All research staff are CITI-certified and will receive regular training at lab meetings regarding the importance of confidentiality of data.

Biological specimen tubes containing plasma, serum, DNA, and urine will be tagged with study ID#'s only and will not include any protected health information. Specimens will be stored in locked freezers at each of the three sites, and will be transported every 3-6 months from MGH and BIDMC to BWH, which will serve as the central biorepository for the study. No protected health information will be shared with collaborators outside of Mass General Brigham. Genetic data will not be placed onto publicly available repositories such as the National Institutes of Health (NIH) central repository.

8. POTENTIAL BENEFITS

8.1 Potential benefits to participating individuals

Individuals assigned to receive DFO may experience lower rates of postoperative AKI following cardiac surgery. Our hypothesis that iron chelation with DFO may prevent/attenuate AKI in patients undergoing cardiac surgery is supported by ample data from preclinical studies, as well as preliminary data in humans (discussed in detail in section 1).

8.2 Potential benefits to society

This study will help answer a critically important question about the potential pathologic role of iron in AKI. If we demonstrate a therapeutic effect of DFO on prevention of AKI or other acute organ injury, the findings from this study will lay the groundwork for conducting a larger, phase 3, RCT of iron chelation in the setting of cardiac surgery. Even null findings will yield important scientific insights into AKI. We will generate novel data on circulating measures of inflammation and oxidative stress in the perioperative setting, which we will explore in relation to clinical endpoints such as AKI. Using sophisticated translational immunology techniques, including flow cytometry and RNA-Seq, we will generate novel data on monocyte immunophenotype in the setting of AKI.

9. MONITORING AND QUALITY ASSURANCE

9.1 Independent monitoring of source data

Study investigators collecting the data will be blinded to the treatment group. The key linking the study ID with the treatment group will be maintained securely by the study's biostatistician and by the research pharmacies of each of the three participating sites.

9.3 Safety monitoring and reporting

Overview

The patients in this study will be undergoing high risk surgery and will be critically ill postoperatively. It is therefore expected that they will have a number of unrelated adverse health events during the course of their hospital stay. Therefore, we will limit the scope of our adverse events (AEs) monitoring and reporting to the following AEs of special interest (AESI), which will be assessed by review of electronic medical records: hypersensitivity reactions (including anaphylaxis); hypotension; ARDS; infection/sepsis; and any AE that, in the view of the site PI, is definitely or possibly related to the study drug.

Hypersensitivity reaction

During the 12h study drug infusion, patients will be in the highly monitored setting of the operating room or the cardiothoracic ICU. If a patient develops anaphylaxis or any other serious AE during the study drug infusion that is related or possibly related to the study drug, the infusion will be discontinued

immediately. If a patient develops anaphylaxis, the patient will be treated as per routine clinical care, including IM epinephrine, methylprednisolone, antihistamines, normal saline, albuterol, and other therapies as determined by the clinical team.

Hypotension

Although hypotension has not been reported with the DFO dosing regimen that will be used in the current study, we will monitor the frequency and severity of hypotension in the perioperative period by calculating the vasoactive-inotropic score during the first 24 hours of the study, beginning with the start of the study drug infusion. The vasoactive-inotropic score is a validated method for integrating all vasoactive medications and their doses on an hourly basis into a single measure, and has been used in multiple settings,¹¹¹⁻¹¹³ including CPB surgery.¹¹⁴

ARDS

The incidence of ARDS will be assessed daily during the hospital stay for a maximum of 7 days. ARDS will be defined and its severity categorized according to the Berlin criteria¹¹⁵ as follows:

Berlin Definition of ARDS	
Timing	Within 1 week of a known clinical insult
Chest imaging (chest radiograph or computed tomography)	Bilateral opacities – not fully explained by effusions, lobar/lung collapse, or nodules
Origin of edema	Respiratory failure not fully explained by cardiac failure or fluid overload Need objective assessment (e.g., echocardiography) to exclude hydrostatic edema if no risk factor present
Oxygenation	
Mild	$\text{PaO}_2/\text{FiO}_2$ 201-300 mm Hg with $\text{PEEP} \geq 5 \text{ cm H}_2\text{O}$
Moderate	$\text{PaO}_2/\text{FiO}_2$ 101-200 mm Hg with $\text{PEEP} \geq 5 \text{ cm H}_2\text{O}$
Severe	$\text{PaO}_2/\text{FiO}_2 \leq 100 \text{ mm Hg}$ with $\text{PEEP} \geq 5 \text{ cm H}_2\text{O}$

Abbreviations: FiO_2 , fraction of inspired oxygen; PaO_2 , partial pressure of arterial oxygen; PEEP , positive end-expiratory pressure

In addition to monitoring the incidence and severity of ARDS, we will also record the frequency of the following respiratory outcomes to further monitor for pulmonary toxicity that may not meet the strict criteria for ARDS:

- Requirement for mechanical ventilation >24h postoperatively
- Ventilator-free days to day 28

Infection/sepsis

We will document all suspected or confirmed infections in the first 7 days or until hospital discharge. Infections will be categorized according to the source (pneumonia, genitourinary, biliary, bacteremia, sternal wound infection, or other) and severity (infection alone, sepsis, or septic shock). Sepsis is defined as life-threatening organ dysfunction caused by a dysregulated host response to infection. Organ dysfunction is defined as an acute increase in the total SOFA score ≥ 2 points consequent to the infection.⁹⁴ Septic shock is defined as sepsis with persistent hypotension requiring vasopressors to maintain mean arterial pressure $\geq 65 \text{ mm Hg}$ and having a serum lactate level $> 2 \text{ mmol/L}$ despite adequate volume resuscitation.⁹⁴

Classifying AESI according to severity and relatedness to the study intervention

For each AESI, site PIs will document the severity and relatedness to the study intervention. Severity of AESIs will be assessed using the Common Terminology Criteria for Adverse Events (CTCAE) v5.0. Relatedness will be categorized as definitely, possibly, or not related to the study intervention, according to the following definitions:

- **Definitely Related:** The adverse event is clearly related to the investigational agent – i.e., an event that follows a reasonable temporal sequence from administration of the study intervention, follows a known or expected response pattern to the suspected intervention, or that is confirmed

by improvement on stopping the exposure and that could not be reasonably explained by the known characteristics of the subject's clinical state.

- Possibly Related: An adverse event that follows a reasonable temporal sequence from administration of the study intervention and follows a known or expected response pattern to the suspected intervention, but that could readily have been produced by a number of other factors.
- Not Related: The adverse event is clearly not related to the investigational agent – i.e., another cause of the event is most plausible; and/or a clinically plausible temporal sequence is inconsistent with the onset of the event and the study intervention and/or a causal relationship is considered biologically implausible.

Reporting of unanticipated problems, including unanticipated AEs

Site PIs will report all unanticipated problems involving risks to subjects or others to the overall study PI, [name], within 24h of the date they first become aware of the problem. [name] will report all unanticipated problems involving risks to subjects or others to the Mass General Brigham Institutional Review Board (IRB), which is serving as the single IRB for this study, and to the Chair of the Data and Safety Monitoring Board (DSMB), within 5 working days/7 calendar days of the date he first becomes aware of the problem. Other AEs and minor protocol deviations will be reported to the IRB during continuing review.

Unblinding

Physicians caring for study subjects in an emergency situation may determine that unblinding is necessary for clinical care. In such a scenario, physicians may be unblinded. Whenever possible, the physician caring for the patient should contact the site PI to notify them of the need to be unblinded to a particular subject and communicate any planned intervention so that such interventions can be documented. Physicians can be unblinded by contacting the research pharmacy at their site (available by phone/pager 24h/day, 7d/week) and requesting to be unblinded for provision of emergency care.

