Exclusion Criteria	
 1. AKI, defined as any of the following: 
 ▪ Increase in serum creatinine \geq0.3 mg/dL in 48h ▪ Increase in serum creatinine \geq50% in 7d (if no value available in last 7d, use most recent value in last 3 months) ▪ Urine output \leq0.5 ml/kg/h \times 6 consecutive hours (only assessed in patients with hourly monitoring via Foley catheter) ▪ Receipt of renal replacement therapy (RRT) within 7d 2. Advanced chronic kidney disease (eGFR $<$15 ml/min/1.73m² or end-stage kidney disease receiving RRT) 3. Hemoglobin $<$8 g/dL (closest value in the prior 3 months) 4. Fever (temperature \geq38°C) in the last 48h 5. Suspected or confirmed bacteremia, endocarditis, or pyelonephritis 6. Pneumonia, aspiration, or bilateral pulmonary infiltrates from an infectious etiology reported on chest x-ray or CT scan in the last 7d 7. Positive COVID-19 test in the last 10d 8. Previous iron chelation therapy (including prior participation in DEFEAT-AKI) 9. Known hypersensitivity to DFO 10. Taking prochlorperazine 11. Known severe hearing loss 12. Pregnant or breastfeeding 13. Prisoner 14. Concurrent participation in another interventional research study in which the intervention has potential interaction with DFO 15. Surgery to be performed under conditions of circulatory arrest 16. Receiving extracorporeal membrane oxygenation 17. Durable ventricular assist device (VAD) prior to surgery (does not include Impella device or intra-aortic balloon pump) 18. Any condition which, in the judgement of the investigator, might increase the risk to the patient 19. Conflict with other research studies
Number of Subjects	330
Length of Participation	Until hospital discharge

Interventions	Deferoxamine 30 mg/kg (max total dose, 6g) or an equal volume of normal saline placebo administered as a continuous intravenous infusion over 12h, beginning immediately prior to cardiac surgery

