5.2 Data to be collected

Upon enrollment, the following variables will be recorded: age; sex; race; ethnicity; comorbidities; home medications; type of surgery; urgency of surgery (elective, urgent, or emergent); and date of surgery. The following data will be recorded postoperatively:

- Cardiopulmonary bypass (CPB) time
- Aortic cross clamp time
- Estimated blood loss intraoperatively
- Requirement for (and number of) red blood cell transfusions intraoperatively and for 7d
- Requirement for (and volume) of Cell Saver used intraoperatively
- Duration of invasive mechanical ventilation
- Myocardial injury, atrial fibrillation, ARDS, and infection/sepsis within 7d
- Physiologic and vital sign data, including heart rate, blood pressure, and urine output for 7d
- Daily lab values, including hemoglobin and serum creatinine, for 7d
- Receipt of renal replacement therapy within 7d
- Reoperation during hospitalization
- ICU and hospital length of stay
- ICU and hospital mortality

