7. RISKS AND DISCOMFORTS

Overview of DFO safety profile

DFO was the first iron chelator approved by the FDA (in 1968), and thus has a long track record of safety. DFO is generally very well tolerated, as patients with genetic hemoglobin disorders complicated by iron overload often receive DFO on a daily basis for their entire lives.¹⁰³ Rare but serious potential adverse effects of DFO include hypersensitivity reactions, hypotension, acute respiratory distress syndrome (ARDS), infection, vision changes, and hearing loss.

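### Vision changes and hearing loss are listed as serious harms but are not named AESIs, so they count only if judged drug-related; the infection window is also stated inconsistently

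*Combined protocol and SAP*

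**What the plan says.** Section 7 of the combined protocol and SAP opens its account of DFO safety with this list: "Rare but serious potential adverse effects of DFO include hypersensitivity reactions, hypotension, acute respiratory distress syndrome (ARDS), infection, vision changes, and hearing loss". Each of the six then has its own subsection (7.1 to 7.6), and known severe hearing loss is an exclusion criterion in section 3.2.

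Section 9.3 argues that unrelated events will be common after high-risk surgery, and so "we will limit the scope of our adverse events (AEs) monitoring and reporting to the following AEs of special interest (AESI"). The list, to be filled by review of electronic medical records, reads "hypersensitivity reactions (including anaphylaxis); hypotension; ARDS; infection/sepsis; and any AE that, in the view of the site PI, is definitely or possibly related" (meaning related to study treatment). For each AESI the site PI then grades severity, and "Relatedness will be categorized as definitely, possibly, or not related to the study intervention".

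On infection, section 9.3 states: "We will document all suspected or confirmed infections in the first 7 days or until hospital discharge". The data list in section 5.2 has "Myocardial injury, atrial fibrillation, ARDS, and infection/sepsis within 7d". For comparison, the ARDS text in section 9.3 reads "The incidence of ARDS will be assessed daily during the hospital stay for a maximum of 7 days". The synopsis gives length of participation as "Until hospital discharge".

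**The concern.** The list of serious harms and the list of monitored harms do not match, and no reason is given for the two omissions. The omission also changes the rule for counting an event. For the four named harms, occurrence is enough and relatedness is judged afterwards. For vision and hearing, the relatedness judgement decides whether the event is recorded as an AESI at all.

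Section 9.4 gives the DSMB the option of unblinded adverse event review. An arm comparison is more informative than a blinded single-case judgement, but events judged unrelated would have been filtered out before the DSMB could make it. Section 8.2 presents the trial as groundwork for phase 3, so a low or zero count for these two harms could later be read as reassurance that the method of collection does not fully support.

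On infection, two sites could apply different cut-offs to patients still in hospital after day 7, and each could cite the protocol for doing so.

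**Working it through.** **Step 1. Compare the lists.** The last column gives the frequency band of the closest entry in section 7.7; the matching of entries is mine.

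| Harm in section 7 | Named AESI in 9.3 | Recorded if judged not related | Band in 7.7 |
|---|---|---|---|
| Hypersensitivity (7.1) | Yes | Yes | below 1/10,000 |
| Hypotension (7.2) | Yes | Yes | 1/1,000 to 1/10,000 |
| ARDS (7.3) | Yes | Yes | below 1/10,000 |
| Infection (7.4) | Yes | Yes | 1/1,000 to 1/10,000 |
| Vision changes (7.5) | No | No | 1/1,000 to 1/10,000 |
| Hearing loss (7.6) | No | No | 1/100 to 1/1,000 |

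Four of six are named. Frequency does not explain the choice: hearing disturbance sits in a higher band than the entries matching all four named harms, and vision shares a band with two of them.

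**Step 2. How much discretion does the catch-all leave?** Under the definitions in section 9.3, an event is possibly related if its timing is reasonable and it fits a known pattern, even when other factors could readily explain it. It is not related if another cause is the most plausible one, or if a causal link is biologically implausible. A hearing complaint after bypass surgery could meet either definition, so recording depends on the site PI's choice.

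**Step 3. Expected counts.** Inputs: 300 analyzable patients (section 6.6) randomized 1:1 (section 4.3), so 300 / 2 = 150 on DFO; bands from section 7.7. Assumption: those general bands apply to a single 12-hour infusion.

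Expected cases = 150 × p. Probability of at least one = 1 − (1 − p)^150.

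- Hearing, p = 1/1,000: 0.15 cases; probability 13.9%.
- Hearing, p = 1/100: 1.5 cases; probability 77.9%.
- Vision, p = 1/10,000: 0.015 cases; probability 1.5%.
- Vision, p = 1/1,000: 0.15 cases; probability 13.9%.

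As a cross-check, section 7.6 cites 1 of 144 DFO patients with hearing loss in the intracerebral hemorrhage trial: 150 × 1/144 = 1.04 cases.

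**Step 4. What a zero count would show.** With 0 of 150, the one-sided 95% upper bound is 1 − 0.05^(1/150) = 1.98%, about 2.0%. This assumes that every event is captured. If only a fraction s is captured, the bound on the true rate is 1.98% / s. The documents give no value of s. For illustration, s = 0.75 gives 2.6% and s = 0.5 gives 4.0%.

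**Step 5. The infection window.** The section 9.3 sentence does not say which limit governs.

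- Earlier of the two limits: capture ends at day 7, or sooner if the patient is discharged sooner. This fits section 5.2 and mirrors the ARDS rule.
- Through discharge: capture continues past day 7 for patients still in hospital. This fits the length of participation in the synopsis but not section 5.2.

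The readings part only for patients in hospital after day 7. The documents do not give that share, so the difference cannot be sized.

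**The case against.** The strongest reply is that the catch-all already covers both harms. Its threshold is low, and sections 7.5 to 7.7 describe vision and hearing effects as known effects of DFO, so a charted new disturbance soon after the infusion would often qualify. This largely stands: the two harms are not excluded, and the gap is confined to events judged unrelated and events never charted. It does not close the gap, because the same sections tie these harms mainly to high doses or years of exposure. That gives a site PI a ready reason to call an event after one infusion unrelated.

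A second reply is that naming the acute harms is a reasoned priority. The five hearing-loss patients cited in section 7.6 had a mean exposure of 15 years. Section 7.5 says that no vision changes were described in the short-term studies, and the cited hemorrhage trial had hearing loss in 1 of 144 versus 1 of 147. This stands as a reason to expect few events, and with so few the trial will say little about any difference between arms. It is not a reason to record them under a stricter rule than the other four.

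A third reply is that section 9.3 sends other adverse events to the IRB at continuing review. That is a reporting route. The same section restricts what is monitored, so it does not establish systematic capture.

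A reader might infer that the trial could not report vision or hearing rates by arm. The documents do not support that. Investigators are blinded (sections 4.3 and 9.1), so the filter should act alike in both arms, and rates of charted, possibly related events can be reported. They would be under-ascertained.

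A reader might also infer that infection recording stops at day 7. That is one reading of section 9.3. The ARDS text carries an explicit maximum and the infection sentence does not, and a later infection judged possibly related would still fall under the catch-all, which has no day limit.

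**Conclusion.** The point holds in a limited form. Two of the six harms that section 7 calls serious are not named AESIs, and they are counted under a narrower rule than the other four. The likely result is under-ascertainment in both arms, with no reason to expect it to favor one arm while blinding holds. Few events are at stake: 0.15 to 1.5 hearing cases and 0.015 to 0.15 vision cases among 150 DFO patients, if the general bands carry over to one infusion. The true figures could be lower, given the short exposure. The main consequence is for interpretation: a zero or near-zero count would be weaker evidence of safety than it appears.

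The infection window is an inconsistency between sections 9.3 and 5.2, of unknown size. It is not a demonstrated loss of events after day 7. Neither matter affects the primary endpoint, the sample size or treatment.

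**What to change.** In section 9.3, add new hearing disturbance and new visual disturbance to the AESI list. Record both from the existing medical-record review regardless of relatedness, then grade and classify them like the other AESIs. The cost is two extra CRF fields and slightly more chart review.

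This removes the relatedness filter but not the dependence on charting. Asking patients directly would go further, but the documents describe no baseline counterpart and establish no suitable study-staff contact, so that is optional.

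Separately, reconcile the infection window between sections 9.3 and 5.2 and state which limit governs safety reporting. If discharge is chosen, section 5.2 must say so, and the cost is chart review for patients still in hospital after day 7. If 7 days is chosen, one clause in section 9.3 is enough. The 7-day sepsis endpoint can stay as it is either way.
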